#### **9.4.4 Optional Visit**

The Sponsor may request that an Optional Visit(s) be conducted at an alternative timepoint.

- Written Informed Consent\*
- Inclusion/ exclusion criteria Part B extension\*\*
- Abdominal area photography
  - If photographs do not meet the Sponsor and/or Photography vendor quality standards, participants will be asked to return to the study site for a reshoot.
- POSAS grading
- Treatment Related Adverse Events assessment

*\*To be performed if first visit of Part B Extension and consent not obtained at Visit 8b.*

*\*\* To be performed if first visit of Part B Extension Visit.*

### **9.5 Efficacy**

#### **9.5.1 Primary Efficacy Variable**

##### **9.5.1.1 POSAS (PI Assessment) – Excisions/Abdominoplasty Incisions (Parts A, B, and B Extension)**

[figure not shown]
The Patient and Observer Scar Assessment Scale (POSAS; Appendix B) will be used to assess the various parameters of each excision site and the abdominoplasty incision. At each observation time point, the PI will grade each scar using the “Observer Scale” of the POSAS. The PI assessment will be conducted after the subject POSAS assessment so as not to influence the subject’s grading.

#### **9.5.2 Secondary Efficacy Variables**

##### **9.5.2.1 POSAS (Subject Assessment) – Abdominoplasty Incisions (Parts B and B Extension)**

At each observation time point, the subject will be directed to grade the left and right side of the incision scar separately using the “Patient Scale” criteria of the POSAS. Then, each side of the abdominoplasty incision (left and right) will be divided into 5cm sections starting from the midpoint moving outwards to the end of the incision. The subject will use the “Patient Scale” criteria of the POSAS to assess the middle 3cm section within each 5cm section of the incision

line. Sections that are less than 5cm (as well as their paired contralateral section) will not be assessed (Refer to Figure 6). After the subject has completed his/her grading, the PI will grade the incisional scar using the “Observer Scale” of the POSAS.

**Figure 6. 5cm sections of Abdominoplasty Incision**

#### **9.5.2.2 POSAS (PI assessment) – Abdominoplasty 5 cm sections (Parts B and B Extension)**

Using a standard clear plastic 15 cm ruler and surgical marker, each side of the abdominoplasty incision (left and right) will be divided into 5cm sections starting from the midpoint moving outwards to the end of the incision. Markings will be placed 2 cm below the scar incision in order to not obstruct the scar. The PI will use the POSAS to assess the middle 3cm section within each 5cm section of the incision line. Sections that are less than 5cm (as well as their paired contralateral section) will not be assessed (Refer to Figure 6).

Photography will be taken of each individual section including those that are less than 5 cm (as well as their contralateral section) in order to obtain photographs of the scar terminus. A 5cm adhesive ruler will be adhered at least 2 cm underneath each 5 cm section in order to confirm accuracy of the 5cm markings. Pre- identified labels (i.e., L1, L2, L3, etc.) will be adhered directly above each section.

#### **9.5.2.3 Independent Panel Review - Photography**

At each observation time point, close-up photographs of each excision will be taken. Upon study completion, a panel of raters will review the photographs in a blinded fashion. Assessors will grade scars using the “Observer Scale” of the POSAS (pliability and vascularity will not be assessed).

#### **9.5.2.4 Histology**

Study Part A only. Histologic appearance of excision sites will be assessed and compared. Logistics and assay specifics will be provided in a separate manual.

#### **9.5.2.5 Tensile Strength**

Study Part A only. *Ex vivo* tensile strength of excision sites will be assessed and compared. Logistics and assay specifics will be provided in a separate manual.

### **9.5.3 Exploratory Efficacy Variables**

#### **9.5.3.1 POSAS (Subject Assessment) – Excisions (Part A)**

At each observation time point during study Part A, the subject will be directed to grade each excision scar separately using the “Patient Scale” criteria of the POSAS. After the subject has completed his/her grading, the PI will grade each excision scar using the “Observer Scale” of the POSAS.

## **9.6 Safety**

### **9.6.1 Clinical Safety Laboratory Tests**

Standard clinical laboratory analyses (CBC/Diff, chemistry) will be conducted on blood samples collected at Screening V1a, V4a (Day 29), V5a (Day 57 - Group 2 only), V6a (Day 85 - Group 1 only), V3b (M1) and at study exit.

Clinically significant results, in the opinion of the PI, should be reported as AEs. If an AE requires laboratory testing, the results of the test must be obtained by the investigative site and filed in the subject’s documentation.

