## 1 INTRODUCTION

SLI-F06 is a synthetic 40-amino acid peptide that is being developed as a treatment to promote wound healing and improve scar appearance. The amino acid sequence of SLI-F06 is derived from an endogenous human protein that has been shown in animal models to promote accelerated wound healing, reduced scarring, and increased wound tensile strength. In these same animal models, the SLI-F06 has been demonstrated to retain similar pro-migration, pro-tensile strength, and anti-fibrotic properties as the endogenous protein.

SLI-F06 drug product (DP) is a sterile lyophilized powder consisting of SLI-F06 as the active ingredient and formulation buffer components. The DP will be reconstituted in clinic with USP Water for Injection and injected intradermally along both edges of a freshly made excision to achieve a primarily local effect.

The route of administration, dosage, dosage regimen and treatment period for the current study are based on large and small animal safety and efficacy studies. Pre-clinical toxicology testing of SLI-F06 includes a 5-day intravenous repeat dosing in rats, a 3-day subcutaneous repeat dosing in pigs, and a 3-day intradermal repeat dosing in a wounded pig model. The intended human drug exposure for the current study is far below the human equivalent dose that has demonstrated to be safe in animals. Please see the Investigator Brochure for a summary of all preclinical studies as well as a list of references.

The study population will consist of healthy patients planning to undergo elective abdominoplasty. During Part A of this study (i.e., Phase I Safety/Proof of Concept), each subject will receive 12, 14, or 18 small or large excisions at 8 weeks or 12 weeks pre-abdominoplasty. Wounds treated with SLI-F06 or vehicle will be followed until the time of abdominoplasty when the tissue is harvested. At the completion of study Part A, subjects will enter study Part B where they will undergo the abdominoplasty, have the abdominoplasty incision treated with SLI-F06, and be followed for an additional 12 months. At the completion of Part B, subjects will be invited to participate in the study Part B Extension where the abdominoplasty scar will be monitored for an additional 12 months.

This is a first-in-human study; there are currently no human experience or regulatory actions related to SLI-F06. The study will be conducted in compliance with the protocol, Good Clinical Practices, and all applicable regulatory requirements.

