## 2 STUDY OBJECTIVES

The primary objectives of this study are the following:

- Part A: Assess the safety and tolerability of SLI-F06 in the treatment of planned surgical excisions.
- Part B: Assess the safety and tolerability of SLI-F06 in the treatment of abdominoplasty incisions.
- Part B Extension: Assess the efficacy of SLI-F06 treatment on the appearance of abdominoplasty incision scars.

Secondary objectives include, but are not limited to, the following:

- Part A:
  - Assess the effect of SLI-F06 on scar appearance.
  - Assess the effect of SLI-F06 on wound strength.
  - Assess the effect of SLI-F06 on histological appearance of scars.
  - Assess immunogenicity effects of SLI-F06.
- Part B:
  - Assess the effect of SLI-F06 on post-operative abdominoplasty scar appearance.
  - Assess immunogenicity effects of SLI-F06.
- Part B Extension:
  - None

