### **9.6.2 Immunogenicity Testing**

During Study Part A, immunogenicity analyses will be conducted on blood samples collected from subjects at Screening V1a, V3a (Day 8), V4a (Day 29), V5a (Day 57) and V6a (Day 85 - Group 1 only). During Study Part B, immunogenicity analyses will be conducted at V2b (Day 8), V3b (M1), V4b (M2), V5b (M3), V6b (M6), V7b (M9), and V8b (12M).

Logistics and assay specifics will be provided in a separate manual.

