#### **9.6.3.2 Documenting Adverse Experiences**

During Parts A and B, the PI is responsible to document all AEs that occur during the study. AEs should be documented as a single medical diagnosis. When this is not possible, AEs should be documented in terms of signs/symptoms observed by the PI or reported by the subject at each study visit. Each AE that appears to be independent of any prior event will be reported separately.

All AEs occurring after the subject first exposure to SLI-F06 through the last study visit must be reported, regardless of AE causality. All AEs, whether in response to a query, observed by the study site personnel, or reported spontaneously by the subject, will be recorded. Any clinically significant AEs deemed related to treatment reported or observed at the final study/treatment visit will be followed until stabilization or resolution (or up to 30 days after final study visit).

At each visit during the study, the subject will be assessed for the occurrence of new and ongoing AEs. The following data will be collected on all AEs and recorded on the appropriate CRF:

- Event name (diagnosis preferred, if unknown, record the signs/symptoms)
- Onset date and end date
- Maximum intensity (severity)
- Seriousness
- Action taken regarding study drug
- Corrective treatment, if given
- Outcome
- PI's assessment of causality

Vital sign abnormalities are to be recorded as AEs only if they are clinically significant (for example: are symptomatic, requiring corrective treatment, leading to discontinuation or fulfilling a seriousness criterion).

For findings considered typical of minor excisional surgery that persist or become more severe than expected, the investigator should determine:

- The start date – when the finding exceeds what may be typically seen with minor excisional surgery.
- Maximum intensity (severity) – using the definitions for adverse event severity found in section 9.6.3.4, the investigator should assign a severity to the adverse event. For events that change in severity, the maximum severity attained should be recorded.

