### 10.3 Assessment of Safety

For Parts A and B, safety analysis will be conducted on the Safety Population (SAFT), by tabulations of AEs, safety laboratory parameters and immunogenicity outcomes.

Subjects will be followed for AEs (local and systemic) throughout the study. Events specific to treatment sites will be recorded by excision site (Study Part A) and per side (Study Part B) to allow comparison of study treatments.

For Part B Extension, Safety analysis will be conducted on the ITT population. Subjects will be followed for Treatment-Related AEs (local and systemic) throughout the study.

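### No scheduled CBC or chemistry sample falls earlier than about four weeks after either injection session, although blood is already drawn at Day 8 in both parts

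*Protocol*

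**What the plan says.** The Introduction states: "This is a first-in-human study". Section 2 gives the primary objectives as "Part A: Assess the safety and tolerability of SLI-F06 in the treatment of planned surgical excisions" and "Part B: Assess the safety and tolerability of SLI-F06 in the treatment of abdominoplasty incisions".

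SLI-F06 is injected in one session per part: at Visit 2a (Day 1, section 9.2.2) and at Visit 1b (Day 0, section 9.3.1).

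For the safety panel (CBC with differential, and chemistry), section 9.6.1 says the analyses "will be conducted on blood samples collected at Screening V1a, V4a (Day 29". It then lists V5a for Group 2 or V6a for Group 1, V3b at Month 1, and study exit.

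For immunogenicity, section 9.6.2 uses "blood samples collected from subjects at Screening V1a, V3a (Day 8), V4a (Day 29" and later visits in Part A. For Part B it says that "immunogenicity analyses will be conducted at V2b (Day 8), V3b (M1" and onward to Month 12.

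The visit lists agree. Sections 9.2.3 (V3a) and 9.3.2 (V2b) include immunogenicity sampling but no safety panel. The first panels after injection are listed in 9.2.4 (V4a) and 9.3.4 (V3b).

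Section 10.3 plans the safety analysis of Parts A and B "by tabulations of AEs, safety laboratory parameters and immunogenicity outcomes".

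**The concern.** Laboratory parameters are one of the three components that section 10.3 names for the safety analysis. After a one-time local injection, a systemic effect on blood counts or chemistry, if there is one, may well be short. A first look at about four weeks can show what persists or appears late. It cannot show a change that comes and goes in the first weeks.

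Section 9.6.1 also covers laboratory tests that an adverse event requires. That route depends on something clinical prompting the test, so it does not reach a silent change. In a first-in-human study the missing early look matters most for exactly that kind of finding. The gap is avoidable, because subjects already attend and give blood at Day 8 in both parts.

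**Working it through.** **Inputs**

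| Item | Part A | Part B | Section |
|---|---|---|---|
| Injection | Day 1 (V2a) | Day 0 (V1b) | 9.2.2, 9.3.1 |
| First safety panel after injection | Day 29 ± 2 (V4a) | Month 1 ± 3 days (V3b) | 9.2.4, 9.3.4, 9.6.1 |
| Earlier blood draw, immunogenicity only | Day 8 ± 1 (V3a) | Day 8 ± 1 (V2b) | 9.2.3, 9.3.2, 9.6.2 |
| Subjects | about 25 | all who complete Part A | 10.1, Synopsis |

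**Time from injection to first panel** = visit day − injection day, ± window.

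- Part A: 29 − 1 = 28 days; 28 ± 2 gives 26 to 30 days.
- Part B: taking Month 1 as 30 days (an assumption), 30 − 0 = 30 days; 30 ± 3 gives 27 to 33 days. If a month is taken as anything from 28 to 31 days, the range is 25 to 34 days.

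Scheduled safety panels before those times: none in either part.

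**Time from injection to the Day 8 draw**

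- Part A: 8 − 1 = 7 days; 7 ± 1 gives 6 to 8 days.
- Part B: 8 − 0 = 8 days; 8 ± 1 gives 7 to 9 days.

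**What an earlier look could show (illustration only).** The protocol says nothing on how long a laboratory change might last. Suppose a change peaks at injection and decays exponentially. The share remaining at t days is 0.5^(t / half-life). For the Part A times:

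| Assumed half-life | Left at 7 days | Left at 28 days |
|---|---|---|
| 1 day | 0.8% | below 0.1% |
| 3 days | 20% | 0.2% |
| 7 days | 50% | 6% |
| 14 days | 71% | 25% |

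Day 8 does much better than Day 29 for half-lives of several days to two weeks. For changes over within a few days it also sees almost nothing.

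**Can 25 subjects show anything at Day 8?** If an abnormality is present in a proportion p of subjects when sampled, the chance of seeing at least one case is 1 − (1 − p)^25. For p = 10% this is 93%; for p = 5% it is 72%. A Day 8 panel would therefore be informative for fairly common changes.

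**Number of added panels:** 2 × 25 = 50.

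**The case against.** The schedule contains no contradiction. Section 9.6.1 and the visit lists agree, and the timing is a design choice. That stands.

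A reader might infer that the primary safety objective has no safety data, or no laboratory data, for the early period. The protocol does not support that. Adverse events are assessed on each injection day and at each Day 8 visit. Immunogenicity is a listed safety evaluation and is sampled at Day 8 in both parts. Only the scheduled CBC and chemistry panel is absent.

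Day 8 values would also be hard to interpret. In Part A they follow 12, 14 or 18 excisions under local anaesthetic, and in Part B an abdominoplasty. Every subject receives both SLI-F06 and vehicle, so systemic values have no concurrent control. This stands for both parts and limits attribution. The lack of a concurrent control applies equally to the week-4 panels that the protocol already tabulates, so it does not argue against looking.

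The Introduction describes a mainly local effect and an exposure well below the level found safe in animals, and it refers to the Investigator Brochure. Whether a transient laboratory signal is plausible depends on toxicology not shown here. This also stands, and it keeps the point modest.

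Two further readings go too far:

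- Section 9.6.3.2 says "Vital sign abnormalities are to be recorded as AEs only if they are clinically significant", and no visit list collects vital signs. A reader might call this a rule without data. It is conditional and can apply to abnormalities noted during the monitoring in 6.5.5 and 6.6.1. That monitoring is discretionary or left to standard practice, so no recorded values can be presumed.
- A reader might want section 10.3 to label laboratory results as week 4 onward. Section 9.6.1 already names every sampling visit, so such a label would add nothing.

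**Conclusion.** The point holds as an inexpensive improvement to the design, not as an error. No scheduled CBC or chemistry value exists in the first 26 days after the Part A injections, or in about the first 27 days after the Part B injections (25 if a month is taken as 28 days). An asymptomatic change that resolves within that time would go unseen.

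The schedule facts rest on the protocol alone; the only assumption in the timing is the length of a month. How likely such a change is, and how long it would last, cannot be judged from the protocol, and the half-life figures are illustrative. An analysis plan could not close this gap, because it cannot create samples that the protocol does not schedule.

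**What to change.** Add the existing CBC and chemistry panel to the blood draws already made at V3a and V2b. Amend sections 9.2.3, 9.3.2 and 9.6.1 and the Study Summary table accordingly. The first scheduled laboratory look then falls at 6 to 8 days in Part A and 7 to 9 days in Part B. Existing panels before each injection (screening for Part A; V5a or V6a for Part B) give each subject a value to compare with.

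The cost is about 50 panels and slightly more blood per draw, with no new visit or venipuncture. The report should read the Day 8 results as a check for early changes, not as evidence of cause.

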### **9.6.2 Immunogenicity Testing**

During Study Part A, immunogenicity analyses will be conducted on blood samples collected from subjects at Screening V1a, V3a (Day 8), V4a (Day 29), V5a (Day 57) and V6a (Day 85 - Group 1 only). During Study Part B, immunogenicity analyses will be conducted at V2b (Day 8), V3b (M1), V4b (M2), V5b (M3), V6b (M6), V7b (M9), and V8b (12M).

Logistics and assay specifics will be provided in a separate manual.

### **9.6.3 Adverse Events**

During Parts A and B, all observed or volunteered AEs regardless of treatment group or suspected causal relationship to the study treatment will be recorded in the eCRF. Subjects will be questioned for the occurrence of any new or worsening signs or symptoms at each visit.

During Part B Extension, all Treatment-Related AEs (TRAEs) will be recorded in the eCRF. Subjects will be questioned for the occurrence of any new or worsening signs or symptoms at each visit.

#### **9.6.3.1 Definition of Adverse Event**

An AE is any untoward medical occurrence in a patient or clinical investigation subject administered a medicinal product and which does not necessarily have a causal relationship with the study drug. AEs include any unfavorable and unintended illness, sign, symptom, clinically significant laboratory test abnormality, or disease temporally associated with the use of a medicinal product that has appeared or worsened during the course of the clinical trial, regardless of causal relationship to the study drug(s) under study. AEs include any illness, sign, symptom, or out-of-range and clinically significant laboratory finding that has appeared or worsened during the course of the clinical trial, regardless of causal relationship to the study. Typical signs and symptoms of minor excisional surgery are NOT to be considered adverse events UNLESS:

- They persist longer than expected by the investigator
- They are more severe than expected by the investigator

Findings that should be considered typical of minor excisional surgery include:

- Pain
- Pruritus
- Erythema
- Bruising
- Tenderness
- Crusting/ Scabbing
- Any other finding that the investigator would expect to observe in routine, uncomplicated minor excisional surgery

The collection of non-serious AEs and serious adverse events (SAEs) will begin following the subject's exposure to SLI-F06.

#### **9.6.3.2 Documenting Adverse Experiences**

During Parts A and B, the PI is responsible to document all AEs that occur during the study. AEs should be documented as a single medical diagnosis. When this is not possible, AEs should be documented in terms of signs/symptoms observed by the PI or reported by the subject at each study visit. Each AE that appears to be independent of any prior event will be reported separately.

All AEs occurring after the subject first exposure to SLI-F06 through the last study visit must be reported, regardless of AE causality. All AEs, whether in response to a query, observed by the study site personnel, or reported spontaneously by the subject, will be recorded. Any clinically significant AEs deemed related to treatment reported or observed at the final study/treatment visit will be followed until stabilization or resolution (or up to 30 days after final study visit).

At each visit during the study, the subject will be assessed for the occurrence of new and ongoing AEs. The following data will be collected on all AEs and recorded on the appropriate CRF:

- Event name (diagnosis preferred, if unknown, record the signs/symptoms)
- Onset date and end date
- Maximum intensity (severity)
- Seriousness
- Action taken regarding study drug
- Corrective treatment, if given
- Outcome
- PI's assessment of causality

Vital sign abnormalities are to be recorded as AEs only if they are clinically significant (for example: are symptomatic, requiring corrective treatment, leading to discontinuation or fulfilling a seriousness criterion).

For findings considered typical of minor excisional surgery that persist or become more severe than expected, the investigator should determine:

- The start date – when the finding exceeds what may be typically seen with minor excisional surgery.
- Maximum intensity (severity) – using the definitions for adverse event severity found in section 9.6.3.4, the investigator should assign a severity to the adverse event. For events that change in severity, the maximum severity attained should be recorded.

- The end date – the investigator should record the date that the finding returns to a typical severity or duration, NOT necessarily when the finding is fully recovered. For example, a subject who notes pain well above what would be expected for three days after the procedure but has very minor pain thereafter for six additional days should have an adverse event of pain lasting three days, not pain lasting nine days.

During Part B Extension, the PI is responsible to document all TRAEs that occur during the study. TRAEs should be documented as a single medical diagnosis. When this is not possible, TRAEs should be documented in terms of signs/symptoms observed by the PI or reported by the subject at each study visit. Each TRAE that appears to be independent of any prior event will be reported separately.

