### 6.3 Blinding

To maintain study blind, the Independent Drug Reconstitutor (IDR) (i.e., pharmacist, study nurse or physician not responsible for subject follow-up) will have access to the Randomization Schedule, be aware of treatment assignment, and will prepare study medication. “Injectors”, Investigators, and study coordinators responsible for subject assessment and follow-up, and study subjects will remain unaware of which study treatment was injected on either side of the pannus or abdominoplasty incision, but might not be blinded to the degree of wound tension.

The IDR will consult the Randomization Schedule, prepare syringes of SLI-F06 and vehicle, and label syringes accordingly with the designation of “left side” or “right side”.

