#### **6.5.4 Sequence of Excisions**

Bilateral matched excisions (e.g., R1/L1, R2/L2, etc.) are to be performed in sequence. Each individual excision should be injected and then closed prior to performing the next excision (i.e., do not perform all of the excisions, followed by all of the closures). Injection of study drug is to be performed before closure (i.e., excise skin, undermine if needed, hemostasis, inject study drug, then skin closure).

It is acknowledged that during the excision process, the topography of the pannus will change and the final placement, orientation, and number of excisions may not match pre-defined pannus mapping. In such cases, the abdominoplasty map should be updated and annotated accordingly in order to match the final placement, orientation, and number of excisions.

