#### **6.5.6 Anesthetic Preparation and Administration**

At each excision site, local injections of dilute anesthetic solution with epinephrine should be used as per the site's standard practice (e.g., 0.05-0.1% lidocaine with ~1:1,000,000 epinephrine) with or without sodium bicarbonate. Use of dilute anesthetic solutions containing epinephrine is suggested in order to optimize hemostasis. Total lidocaine dosage should not exceed established lidocaine guidelines of 7 mg/kg with respect to mg lidocaine per kg patient weight. Use of 1% rather than 2% is suggested to minimize over-dosing errors.

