#### 10.3.1 Adverse Events

All AEs occurring during the study will be recorded and classified on the basis of MedDRA terminology. Descriptions of AEs will include the date of onset, the date the AE ended, the severity of the AE, the relationship to study medication, the action taken regarding study medication usage, the action taken to treat the AE, and the outcome. All reported treatment-emergent AEs (TEAEs) will be summarized by the number of Subjects reporting AEs, system organ class, severity, seriousness, and relationship to study medication. TEAEs are those AEs with an onset on or after the date of initial IP exposure.

AEs will be summarized by treatment group and severity, and by treatment group and relationship to IP. Each subject will be counted only once within a system organ class or a preferred term by using the AEs with the greatest relationship within each category.

All information pertaining to AEs noted during the study will be listed by subject, detailing verbatim given by the PI, preferred term, system organ class, start date, stop date, severity, actions taken, and drug relatedness.

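### The protocol gives conflicting starts for AE and SAE collection; read literally, 9.6.3.1 and 9.6.3.2 leave out Day 1 events with onset before the first SLI-F06 injection

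*Protocol*

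**What the plan says.** Two sections fix a start point, and both name the active product. Section 9.6.3.1: "The collection of non-serious AEs and serious adverse events (SAEs) will begin following the subject's exposure to SLI-F06". Section 9.6.3.2: "All AEs occurring after the subject first exposure to SLI-F06 through the last study visit must be reported, regardless of AE causality".

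Other current text is wider. Section 9.6.3: "During Parts A and B, all observed or volunteered AEs regardless of treatment group or suspected causal relationship to the study treatment will be recorded". The first sentence of 9.6.3.2 makes the investigator responsible for documenting every AE during the study. Section 9.6.3.6 asks for all SAEs, related or not. Section 9.2.2 lists an AE assessment at Visit 2a, the excision day, whereas Section 9.2.1 (screening) lists none.

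The analysis section uses a third anchor. Section 10.3.1: "TEAEs are those AEs with an onset on or after the date of initial IP exposure".

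On the order of events at Visit 2a, Section 6.5.4 takes the wounds in right/left matched pairs and says: "Each individual excision should be injected and then closed prior to performing the next excision". On who knows the side, Section 6.3 says that injectors, investigators, coordinators and "study subjects will remain unaware of which study treatment was injected on either side of the pannus or abdominoplasty incision".

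**The concern.** This is a first-in-human study (Section 1), and the Part A primary objective is safety and tolerability (Section 2). The Part A excisions are done only for the study. Optional sedation or nitrous oxide (6.5.5), local anaesthetic with epinephrine (6.5.6), excision and haemostasis (6.5.7) all come before any study injection. The protocol itself recognises a toxicity limit for the anaesthetic: "Total lidocaine dosage should not exceed established lidocaine guidelines of 7 mg/kg". A site that applies the literal start in 9.6.3.1 and 9.6.3.2 could leave a serious reaction in that period unrecorded.

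The anchor also depends on the product. An event with onset after a vehicle injection but before the first SLI-F06 injection is outside the rule, while no event after SLI-F06 can be. Section 10.3 records local events by excision site so that the treatments can be compared, so the start of collection should not depend on which product was injected first. Nor can blinded staff tell, after the first injection, whether the start point has been reached.

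**Working it through.** The protocol gives no figure to reproduce here. The check compares the start rules and then measures the window.

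**1. Start rules side by side**

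| Section | Start of collection or counting | Depends on product? | Event before the first injection on Day 1 |
|---|---|---|---|
| 9.6.3 | Parts A and B, no start point named | No | Recorded |
| 9.6.3.1 | After exposure to SLI-F06 (AEs and SAEs) | Yes | Not collected |
| 9.6.3.2, first sentence | During the study, no start point named | No | Recorded |
| 9.6.3.2, second paragraph | After first exposure to SLI-F06 | Yes | Not required |
| 9.2.2 | AE assessment at Visit 2a | No | Assessed |
| 10.3.1 | Date of initial IP exposure | Only if IP means SLI-F06 alone | Counted, if recorded |

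Sections 9.6.3.1 and 9.6.3.2 are the only collection rules that name a starting event, so a site may reasonably follow them in preference to the general statements.

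**2. How often vehicle is injected first**

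Inputs: about 25 subjects (10.1). All active wounds lie on one side and all vehicle wounds on the other (6.2). The allocation ratio is not stated, so 1:1 is assumed, with 40% to 60% vehicle-first shown as a range.

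- Expected vehicle-first subjects = 25 × p: 25 × 0.5 = 12.5, with a range of 25 × 0.4 = 10 to 25 × 0.6 = 15.
- Chance of at least one such subject = 1 − (1 − p)^25. At p = 0.4 this is 1 − 0.6^25 = 0.999997, and it is higher at p = 0.5 and p = 0.6.

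**3. How long the window is**

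Because wounds run R1/L1, R2/L2 and so on, the first SLI-F06 injection falls at wound 1 or wound 2. Before injection 1, exposure has certainly not begun. After injection 2 it certainly has. The blinded site is in doubt only between the two. Wounds handled after the first pair = n − 2:

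- 12 wounds: 10 of 12 (83%)
- 14 wounds: 12 of 14 (86%)
- 18 wounds: 16 of 18 (89%)

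So at most one or two wounds are excised before the first SLI-F06 injection. If anaesthetic is given wound by wound, the same counts apply to it. If all wounds are numbed beforehand, the whole anaesthetic period falls before exposure; the protocol does not fix this order. Section 6.5.4 also accepts that the final placement and number of excisions may depart from the map, so the pair sequence is itself a condition.

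**4. Date against clock time**

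All of this happens on Day 1, and 9.6.3.2 lists the onset date, not the time, among the AE data. Under the date rule in 10.3.1, any recorded Day 1 event is treatment-emergent. The gap is therefore in collection, not in the analysis definition.

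**5. Meaning of IP**

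Exclusion criterion 2 in Section 5.2.1 and the heading of 7.1 equate IP with SLI-F06. Section 6.5.8, whose heading refers to administering investigational product, covers SLI-F06 or vehicle. If IP includes vehicle, a subject stopped after one vehicle wound is in the safety population (10.4.2) yet never reaches the collection start in 9.6.3.1. If it does not, that subject is in neither.

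**The case against.** The strongest reply is that a sensible site would record these events anyway. Section 9.6.3, the opening of 9.6.3.2, the Visit 2a assessment and the SAE rule in 9.6.3.6 all use wider wording, and the blinded site knows the date of exposure even if not the minute. This stands in part. It shows that loss of data is not certain, but it does not remove the contradiction.

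Several stronger readings are tempting, and the documents do not support them.

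- A reader might infer that all events caused by anaesthesia, excision or vehicle fall outside collection. Only events with onset before the first SLI-F06 injection do. Later-onset events are reportable regardless of causality.
- A reader might infer that blinded staff can never tell whether exposure has begun. The doubt is confined to the interval between the two injections of the first pair, if the sequence is followed.
- A reader might infer that a subject stopped after a vehicle wound would have no AE record at all. That ignores the wider text.
- A reader might infer that the asymmetry hides harm from SLI-F06. It can drop only events from before SLI-F06 is given, including vehicle events, and this would not make SLI-F06 look safer in the comparison.

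Part B adds no new window, because subjects who reach it were already exposed in Part A.

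**Conclusion.** The concern holds as an internal contradiction with a badly chosen anchor, and it should be corrected. Read literally, 9.6.3.1 and 9.6.3.2 leave an uncollected period on Day 1 for every one of the roughly 25 subjects, from the first sedative or anaesthetic to the first SLI-F06 injection. In about 12.5 of them (10 to 15 over the assumed range) that period includes a vehicle injection. It is short and covers at most the first matched pair, provided that the pair sequence is followed and, for the anaesthetic, that numbing is done wound by wound. The documents show that such events could go unrecorded, not that they will. The point still matters because the narrow rule covers SAEs, the procedures are done only for the study, and safety is the primary objective of Part A.

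**What to change.** - In 9.6.3.1 and 9.6.3.2, replace exposure to SLI-F06 with the first study procedure at Visit 2a, so that any sedative or anaesthetic given for the excisions is covered. A blinded site can identify this point, it does not depend on product, and it agrees with 9.6.3 and with the Visit 2a assessment in 9.2.2. Let 9.6.3 refer to the same start.
- Keep the date-based rule in 10.3.1, and state that initial IP exposure means the first injection of either SLI-F06 or vehicle. Use the same meaning in the safety population definition in 10.4.2. A clock-time definition is not needed, because the date rule already counts Day 1 events once they are recorded.

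The cost is wording in a few sections and a few more procedural events in the listings. No trial procedure changes, and no new data field is required.
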